8.3 Enhanced rehabilitation

The main aim of the intervention is to enhance usual rehabilitation by enhancing patients' selfefficacy, and increasing the amount and quality of patients' practice of physical exercise and activities of daily living in order to improve their functional outcomes at 17 and 52 week follow up ²⁴. Self-efficacy will be enhanced by means of a patient held information workbook and diary given to the participant in the acute hospital and kept with them throughout the follow up period of the trial. In addition to whatever community based rehabilitation is provided as part of usual care, we will provide up to six additional therapist (physiotherapist or occupational therapist) or technical instructor sessions to patients once they either return home or are admitted permanently to a care home. The extra sessions will be tailored by the therapists delivering them, and so the total number of sessions used, the time scale for their delivery, and the sessions' content will vary between patients according to clinical need.

The workbook will also include information about what to expect from their recovery and information about NHS, council and voluntary sector services they may be able to use. This will include a variety of community services such as falls preventions programmes. The objectives of the workbook and diary are to:

- 1) Give patients better understanding of what has happened physically to them and to broadly outline what to expect during their recovery.
- 2) Provide information and contact details on rehabilitation services that are available to them as they progress in their rehabilitation (e.g. Intermediate care teams, social services enablement teams, outpatient physiotherapy, falls prevention groups, national exercise referral services). The information will enable patients to ask the therapist they are working with or their GP about available services and what benefit they might offer, and at what stages they would be most beneficial, and to contact the services themselves for more information.
- 3) To enable them to work collaboratively with their therapist to set goals and monitor progress of their rehabilitation in order to improve the quality and the quantity of the physical and activities of daily living exercises they are performing.
- 4) To improve patients' self-efficacy
 - a. To encourage the patient to set goals they want to achieve and to discuss them with their therapist.

- b. To monitor the progress towards/attainment of these goals through keeping a diary of progress. This will provide feedback in the form of both self-reflection and reflection with the therapist. Feedback is recognised as an important component for improving self-efficacy ²⁴.
- 5) To improve communication between hospital and community services, and between the patient and all the different professionals and services with which they come into contact during their rehabilitation.
- 6) To reduce patients' fear of falling by improving self-efficacy for avoiding falls/ exercising, and providing information about local falls prevention services
- 7) To signpost patients to local follow-on community programmes such as exercise referral and falls prevention services with contact details.

Therapists will be trained in each site to deliver the enhanced rehabilitation programme with fidelity. In addition, they will be provided on-going support with e-mails, newsletters and refresher events. New therapists will also be trained if others leave.

8.4 Assessment of Compliance with Trial Treatment/s

This will be considered as part of the process evaluation (Section 9.3.2).

8.5 Concomitant Medications/Treatments

As this is a pragmatic RCT comparing an enhanced rehabilitation programme with usual care, there will be no restrictions on concomitant medications or treatments. Details concerning medication and other treatment use will be collected by the CSRI questionnaire and transcribed into the trial database.

8.6 Who is Blinded to Allocations

Collection of outcome measures, including physical function measures, will be performed blind to treatment allocation by the RPSO. This is a pragmatic trial comparing two rehabilitation interventions, so it will not be possible to blind participants or their clinicians to treatment group allocation. We will include a perception of allocation form for the RPSO to complete, in order to monitor the level of blinding that was achieved for these researchers.

The RPSO will not be informed which group the patient participant has been randomised to and will not be present at any of the therapy sessions. When the RPSO visits the patient participant and carer participant, they will ask the participants before any assessments take place not to reveal trial allocation to the RPSO.

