3.4.2 Secondary Outcome/Endpoints

Secondary endpoints include:

Efficacy:

- 1. Anxiety and depression (HADS) ³⁶
- 2. Cognitive status (AMTS)³³
- 3. Hip pain intensity at (VAS) for hip pain intensity³⁷
- Falls self-efficacy (FES-I) (self-efficacy)^{38,39}
 Fear of falling (VASFoF)⁴⁰
- 6. Physical function (SPPB)^{49,50}
- 7. Grip strength⁴⁶

Carer behaviours may make an important contribution to the intervention's effectiveness. We will also include items to measure care tasks and roles in terms of the type of support provided and the number of hours spent providing support. We will ask about help with the workbook, goal-setting and the practice of rehabilitation exercises as well as more general assistance.

Carer of patient:

- 8. Care-giver strain (CSI)⁵¹
- 9. Care-giver anxiety and depression(HADS)³⁶

Safety:

- 10. Number of adverse events across the two arms
- 11. Number of serious adverse events across the two arms
- 12. Number of re-admissions to hospital following hip-fracture repair surgery

Health Economics:

- 13. Incremental cost-utility ratios, EuroQol EQ-5D-3L (three levels)⁴¹
- 14. Health service and personal social care Cost-utility, (CSRI)⁴³

Process Evaluation:

- 15. Refine the programme theory that was generated from the previous realist review when developing the intervention programme
- 16. Investigate therapists' expectations and experience of implementation, identifying the actual practices, likely tailoring and interactions that took place within the trial setting. Also, investigate therapists' skill level, relevant training, previous experience and level of familiarity of working in this sector. Finally, investigate therapists learning over time and its potential impact on outcomes.
- 17. Investigate the mechanisms driving and shaping the tailoring of the enhanced rehabilitation programme to individual patients and its possible impacts on outcomes.
- 18. Investigate trial participants' experiences and views about their involvement in the FEMuR trial.
- 19. Synthesize all data collected and link it to the explanation of trial findings in relation to the refined programme theory.

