This is a short series of physical function tests which assess lower limb function in terms of balance, gait, strength and endurance. The tests involve: examining the ability to stand with feet together in the side-by-side, semi-tandem and tandem positions; measuring the time to walk 8 feet (2.5m) and the time to rise from a chair and return to the seated position five times. Each test and a summary performance scale obtained by summing the categorical ranking on each test (0-12) were strongly associated with self-reported disability and were independent predictors of short-term mortality and nursing home admission. This was found even at the high end of the functional spectrum in those reporting almost no disability. This battery of tests was designed for use in people's homes and will be administered by the researcher at the 17 and 52 week follow-up assessments.

Health economic measures

EuroQol EQ-5D-3L (three levels)⁴¹

This is a patient-completed index of health-related quality of life, which gives a weight to different health states. It consists of five dimensions: mobility, self-care, usual activities, pain/discomfort, and anxiety/depression. Each has three possible responses. The responses record three levels of severity (no problems, /moderate problems, or severe problems) which is then converted to a health utility weight using UK norms. It also has a VAS ranging from 0 to 100 where the participant draws a line on the scale to rate their health state today. It will be used at baseline and at the 17 and 52 week follow-up assessments, and allows the calculation of quality-adjusted life years (QALY) using the area under the curve method which will be used as part of the economic analysis⁴².

Client service receipt inventory (CSRI)⁴³

The CSRI is a questionnaire for collecting retrospective information about trial participants' use of health and social care services, including voluntary services (e.g. charity services) and the components of the rehabilitation programme. This information will be combined with national sources of reference unit costs^{44,45} in order to calculate health and social care service costs for the economic evaluation. It will be used at baseline and at the 17 and 52 week follow-up assessments as part of the economic analysis. A reduced version of the CSRI will be used at baseline to reduce participant burden as participants are recovering from hip fracture surgery.

Carer completed measure - secondary outcome

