13.1 Source Documents

Source data will be the hospital written and electronic medical records, community electronic and written records, audio-recordings and transcripts of qualitative interviews. The CRF will be considered the source document for data such as questionnaires where no prior record exists and which is recorded directly in the eCRF. Data collected (questionnaires, AEs and other data) will be transcribed into the remote electronic data capture system by the RPSO.

Date(s) of conducting informed consent process including date of provision of patient information, randomisation number and the fact that the patient is participating in a clinical trial (including possible treatment arms) will be added to the patient's medical record chronologically.

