13.2.1 Data processing

All data requested on the eCRF must be entered. All missing data (not entered) will be queried. The database will be designed to allow sites to state whether a data item is not known or not applicable. Personnel at participating sites who are delegated the responsibility for entering data will be assigned unique usernames and passwords for the electronic system. An audit trial of all data entered into the system will be maintained which will log details of any changes made to the data. Data from patient completed questionnaires and demographic data at baseline, 17 weeks and 52 weeks follow-up assessments will be entered onto laptop computers by the RPSO administering the questionnaires. The original patient completed questionnaires will be stored securely at the site.

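### Assessor blinding is not assured: the researcher declared blind also handles forms that can hint at the allocated arm

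*Protocol*

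**What the plan says.** Section 4 specifies blinded outcome assessment, and Section 8.6 assigns it to one role: "Collection of outcome measures, including physical function measures, will be performed blind to treatment allocation by the RPSO". Three measures protect this. The RPSO is not told the allocation, does not attend therapy sessions and, at visits to patient and carer, "they will ask the participants before any assessments take place not to reveal trial allocation to the RPSO". Section 7.6 adds that any randomisation email to the RPSO is a blinded copy. Monitoring is by one instrument: "We will include a perception of allocation form for the RPSO to complete".

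Other sections give the same person further tasks:

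- **Questionnaires.** Under Section 13.2.1, questionnaire data at baseline, 17 and 52 weeks "will be entered onto laptop computers by the RPSO administering the questionnaires".
- **CSRI.** Section 11.5 describes it as capturing health and social care use, "including voluntary services (e.g. charity services) and the components of the rehabilitation programme". On timing: "It will be used at baseline and at the 17 and 52 week follow-up assessments as part of the economic analysis".
- **Adverse events.** Section 13.1: "Data collected (questionnaires, AEs and other data) will be transcribed into the remote electronic data capture system by the RPSO". Section 9.2.1 says the adverse event form records whether the event is related to the intervention.
- **Carers.** Section 3.4.2: "We will ask about help with the workbook, goal-setting and the practice of rehabilitation exercises as well as more general assistance". It does not say who asks.

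**The concern.** Section 8.6 relies on participants keeping their allocation to themselves. That request does little if the RPSO's own forms then ask what rehabilitation the patient received, or show an event marked as related to the intervention.

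Patients and clinicians are unblinded by design, so the RPSO's masking is the only blinding at data collection. If it is lost, expectation could affect how the physical tests are run and scored, and how help is given with the patient-completed scales. The perception-of-allocation form would document a loss of masking but would not prevent it.

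**Working it through.** The check is mainly a comparison of sections.

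1. **Which visits matter.** Section 7.6 requires baseline to be complete before randomisation, so the baseline CSRI cannot reveal the arm. The exposure is at 17 and 52 weeks.

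2. **CSRI.** Sections 11.5 and 13.2.1 together have the RPSO asking about and entering the rehabilitation components. Section 8.3 adds up to six therapy sessions to usual care in the intervention arm, so the answers carry information about the arm. The signal is noisy. The CSRI goes to both arms, and Section 8.2 reports that usual community care varied widely, with some control patients receiving none.

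3. **Adverse events.** Site investigators complete the form and judge causality (Sections 9.2.1 and 10.5). Related serious events go to the CTRC on a separate form (Section 10). Related non-serious events stay on the ordinary form (Section 10.8.1), which the RPSO may transcribe under Section 13.1. The RPSO can therefore see relatedness without judging it. It points to the arm only when an event is judged related.

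4. **Carer items.** The workbook belongs to the enhanced programme (Section 8.3). Section 3.4.2 names no asker, but Section 8.6 has the RPSO visiting carers and Section 13.1 has the RPSO transcribing questionnaires. Reach is limited to patients with a participating carer. In the feasibility trial (Section 3.2.3.1), 31 carers joined alongside 62 patients (31/62 = 50%) and 18 completed follow-up (18/62 = 29%).

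5. **Order and separation.** Sections 9.1 to 9.1.5 list the measures with NEADL first, CSRI eighth, and grip strength and SPPB after it. They are lists and state no sequence. Nothing in the protocol fixes an order, gives these forms to someone else, hides fields from the RPSO, or says whether the same RPSO returns at 52 weeks.

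6. **Which outcomes are exposed.** The researcher administers SPPB and grip strength (Section 11.5), so cues seen before them bear on them directly. Patients complete NEADL (Section 11.4) with help from the blinded researcher (Section 3.4). The RPSO can affect it only through that help and, at 52 weeks, through what was learned at 17 weeks if the same person returns.

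7. **Scale.** The document gives neither an unmasking rate nor a bias, so the following shows only how sensitive the primary analysis would be.
   - The plan's own figure reproduces. Residual SD = 10 × √(1 − 0.52) = 6.93. With two-sided 5% alpha (sidedness is not stated, so this is assumed) and 90% power, n per arm = 2 × (1.960 + 1.282)² × 6.93² / 2.4² ≈ 175.1, rounded up to 176. That is 352 in total, and 352 / 0.79 = 445.6, rounded up to 446. Both match Section 11.2.
   - Standard error of the adjusted difference = 6.93 × √(2/176) = 0.74 points.
   - With a systematic bias b and no true effect, the two-sided rejection rate is 1 − Φ(1.96 − b/0.74) + Φ(−1.96 − b/0.74). For **assumed** b of 0.25, 0.5 and 1.0 points (10%, 21% and 42% of the 2.4-point target) it is about 6%, 10% and 27%, against a nominal 5%.
   - The protocol gives no comparable inputs for SPPB or grip strength.

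**The case against.** A reader might infer that the RPSO is bound to learn the allocation, so that blinded assessment cannot hold. The text does not support that.

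- Section 11.5 speaks of the rehabilitation programme, not specifically the enhanced one. The questionnaires are supplementary documents (Section 19) that are not shown. Therapy contacts reported against variable usual care are a hint, not proof.
- The RPSO does not assess relatedness, and Section 9.2.1 has therapy teams instructed in entering adverse events themselves, so the RPSO is not the only route into the database.
- The carer workbook items may sit with the qualitative researcher, who interviews carers after 17 weeks (Section 9.1.4). The visit schedule lists only CSI and HADS for carers.
- Read as a sequence, the schedule puts NEADL before CSRI at every visit. Carry-over to 52 weeks assumes a returning RPSO who remembers.
- NEADL is reported by unblinded patients, so its main exposure to bias exists whatever the RPSO knows.

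Each of these stands and limits the claim. None removes the conflict: Section 8.6 promises blind collection without qualification, while Sections 11.5, 13.1 and 13.2.1 give the same person forms that can carry allocation cues, with no order or separation to protect the measurements.

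**Conclusion.** The point holds in a limited form: assessor blinding as Section 8.6 states it is not assured. The exposure is clearest for SPPB and grip strength, both secondary outcomes. For the primary outcome it is partial.

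The conclusion rests on the RPSO carrying out the tasks in Sections 13.1 and 13.2.1 as written. The 52-week part also assumes that the same RPSO returns, and the carer part assumes that the RPSO handles those items; the protocol states neither. The size of any bias is unknown, and the rejection rates above illustrate assumed values rather than estimate an effect. The sample size of 446 is unaffected. This is an inexpensive correction worth making, not a defect that invalidates the design.

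**What to change.** Reconcile Section 8.6 with Sections 3.4.2, 9.2.1, 11.5, 13.1 and 13.2.1:

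1. State a fixed order for both follow-up visits: NEADL, the other scales, grip strength and SPPB; then the perception-of-allocation form; then CSRI and adverse event data. The perception form then reflects masking at the time the outcomes were measured.
2. Keep any items specific to the enhanced programme out of the RPSO-administered CSRI. Cost the extra sessions from the session case report forms and therapist electronic records already planned in Section 9.3.2.1. Add a rule against double counting, because patients may report the same contacts in the CSRI.
3. Collect the carer workbook and goal-setting items on a sealed self-completed form returned to the CTRC, or through the qualitative researcher.
4. Have site investigator staff enter the relatedness field, and hide it from the RPSO.

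Ordering alone does not stop carry-over from 17 to 52 weeks, so items 2 to 4 matter even if item 1 is adopted. The cost is form re-ordering, one carer form, an access setting and a de-duplication step in costing, with slightly more missing carer workbook data. No new staff or patient procedures are needed.

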9 PARTICIPANT TIME LINE, ASSESSMENTS AND PROCEDURES

9.1 Schedule for Follow-up

Participant follow-up visits should take place at 17 and 52 weeks post randomisation

Procedures	Screening	Baseline / Randomisation *	Trial intervention**	17 weeks post randomisation Follow-up	Qualitative interviews	52weeks post randomisation Follow-up
Eligibility screening and consent						
Assessment of eligibility criteria	Х					
Written and informed consent (patient / carer))	х					
Confirm consent		Х	Х	Х	Х	Х
Randomisation		Х				
Discharge data		Х				
Outcome measurement - patient						
NEADL		х		Х		Х
HADS		Х		Х		Х
AMTS		Х		Х		Х
VAS hip pain intensity		Х		х		Х
FES-I		Х		Х		Х
VASFoF		Х		Х		Х
EQ-5D-3L		Х		Х		Х
CSRI		Х		Х		Х
Grip strength		Х		Х		Х
SPPB				Х		Х
Outcome measurement - carer						
CSI		Х		Х		Х
HADS		Х		Х		Х
Trial Intervention**			Х			
Qualitative interviews						
Re-affirm consent verbally specifically for qualitative phone interview. (patient / carer)					х	
Qualitative telephone interview					Х	
Safety Event Reporting						
Monitoring of Adverse Events			Х	Х	Х	Х
Monitoring of Serious Adverse Events			Х	Х	Х	Х

* Randomisation and baseline should take place no later than 4 weeks after hip fracture repair surgery

** If randomised to intervention arm.

9.1.1 Baseline

Baseline should be recorded up-to 4 weeks after surgery, in line with timings for obtaining consent.

Participants: Data collection at baseline will include (but not limited to) type of hip fracture, comorbid conditions, Date of surgery, type of surgery, prior living arrangements/place of residence.

Questionnaires administered at baseline will be NEADL, HADS, AMTS, VAS hip pain intensity, FES-I, VASFoF, EQ-5D-3L questionnaire, CSRI, Grip strength.

Carers: Care-giver CSI and care-giver HADS

9.1.2 Discharge

Date of discharge will be recorded, as will place of discharge and place of discharge.

9.1.3 17 Week follow-up

Follow-up visit should occur 17 weeks after randomisation.

Participants: Data collection will include (but not limited to) AEs and RSAEs.

Questionnaires administered will be NEADL, HADS, AMTS, VAS hip pain intensity, FES-I, VASFoF, EQ-5D-3L questionnaire, CSRI, Grip strength, SPPB.

Carers: Care-giver CSI and care-giver HADS.

9.1.4 Qualitative interviews

After the 17 week assessments; Semi-structured telephone interview with participants and carers by the qualitative researcher carrying out the process evaluation. Interviews will be audio recorded.

9.1.5 52 Week follow-up

Follow-up visit should occur 52 weeks after randomisation.

Participants: Data collection will be include (but not limited to) AEs and RSAEs.

Questionnaires administered will be NEADL, HADS, AMTS, VAS hip pain intensity, FES-I, VASFoF, EQ-5D-3L questionnaire, CSRI, Grip strength, SPPB.

Carers: Care-giver CSI and care-giver HADS.

9.2 **Procedures for Assessing Safety**

9.2.1 Process for recording adverse events

All adverse events will be recorded (across both arms) by researchers when they are made aware of the event by the patient, carer, the treating clinicians, or therapists, in accordance with the principles of 'Good Clinical Practice'. Adverse event reporting information will be included in the training given to the therapy teams delivering the intervention and they will be given Instructions on how to enter adverse events on to the trial database. The adverse event form will be completed by investigators at site who will complete information including the seriousness of the event and whether it is related to the intervention. All adverse events will be presented to the Independent Data and Safety Monitoring Committee (IDSMC) periodically. Trial- serious related events will be reported to the CTRC within 24 hours of sites becoming aware. They will also be reported to the IDSMC Chair person and the research ethics committee periodically.

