8.2 Usual rehabilitation care

Usual care consists of a multi-disciplinary rehabilitation delivered by the acute hospital, community hospital and community services depending on patients' individual needs at different times during their recovery and on the availability and accessibility of services in different areas. The multidisciplinary team delivering care and rehabilitation may include at different times: orthopaedic surgeons, orthogeriatricians, nurses, physiotherapists, occupational therapists, dieticians, pharmacists, GPs and social workers. The settings for care include acute orthopaedic or orthogeriatric wards, rehabilitation units in community hospitals, rehabilitation beds in care homes, the patient's own home and care home settings all delivered by a variety of community teams in both health and social care services. The findings from the Phase II feasibility trial were that the provision of usual community-based care was very variable, with some participants in the control group not receiving any community rehabilitation at all.

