10.2 Notes on AE Inclusions and Exclusions

On this study AEs will include the following:

- Non-injurious falls;
- An exacerbation of a pre-existing illness;
- An increase in frequency or intensity of a pre-existing episodic condition;
- A condition (even though it may have been present prior to the start of the trial) detected after the start of the trial; and
- Continuous persistent disease or symptoms present at baseline that worsens during the trial.

The following will not be included as AEs:

- Medical or surgical procedures where the condition which leads to the procedure is the adverse event;
- Pre-existing disease or conditions present before treatment that do not worsen; and
- Overdose of medication without signs or symptoms.

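### The enhanced arm has an extra, trained route for reporting adverse events, so the between-arm event count is liable to be inflated there for mild events such as non-injurious falls

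*Protocol*

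**What the plan says.** Section 3.4.2 lists "Number of adverse events across the two arms" and "Number of serious adverse events across the two arms" as endpoints 10 and 11, and hospital re-admissions as endpoint 12.

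**Common to both arms.** Section 9.2.1 states: "All adverse events will be recorded (across both arms) by researchers when they are made aware of the event by the patient, carer, the treating" (the list of informants goes on to name clinical staff and the therapists). Section 10.8 requires recording for every patient from randomisation to the 52-week assessment. Sections 9.1.3 and 9.1.5 collect adverse events at 17 and 52 weeks without restriction by arm.

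**Enhanced arm only.** Section 9.2.1 adds: "Adverse event reporting information will be included in the training given to the therapy teams delivering the intervention", with instructions for entering events on the trial database. Section 10 repeats this and adds copies of the reporting forms, with the trials unit as an alternative destination. No matching provision is described for usual-care staff. In the section 9.1 schedule, the row "Monitoring of Adverse Events" and the row for serious events are both marked under the trial intervention column, then at 17 weeks, the qualitative interviews and 52 weeks. The footnote to that column reads "If randomised to intervention arm".

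**Contact and event types.** Section 8.3 gives the enhanced arm up to six additional sessions. Section 8.2 reports that the feasibility trial had "some participants in the control group not receiving any community rehabilitation at all". Section 10.2 counts "Non-injurious falls" and exacerbations of existing illness as adverse events.

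**The concern.** A comparison of event counts is fair only if events are looked for equally hard in both arms. Here one arm has an additional group of people who are in the home during recovery, trained to report and told how to enter what they hear. For a control participant without community therapy, the planned contacts that could bring an event to light are the follow-up visits, plus the interview for those sampled. A fall without injury may be forgotten by 17 or 52 weeks, and it leaves little trace in any record.

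Injury or falling during exercise is the risk that section 3.2.5 itself names. An excess of such events in the enhanced arm could be read as harm from the programme when part of it is better detection. The monitoring committee, which under section 12.2 advises on the frequency of safety events, would see the same counts.

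**Working it through.** The protocol gives no event rate, capture rate or target figure for the safety endpoints, so there is no stated figure to reproduce. The check has two parts.

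**1. Routes by which an event can be recorded**

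| Route | Enhanced | Usual care | Section |
|---|---|---|---|
| Researcher told by patient, carer, clinician or therapist | yes | yes | 9.2.1 |
| Collection at 17 and 52 weeks | yes | yes | 9.1.3, 9.1.5 |
| Qualitative interview (sample of 60 patients per arm) | yes | yes | 9.1, 9.3.2.1 |
| Admissions on the service-use questionnaire (CSRI) | yes | yes | 9.3.2.1 |
| Primary and secondary care records | yes | yes | 13.2 |
| Monitoring mark during the intervention period | yes | no (footnote) | 9.1 |
| Trained intervention therapists with forms and database instructions | yes | none described | 9.2.1, 10 |

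The last two rows differ between the arms. The schedule row conflicts with sections 9.2.1 and 10.8. The therapist row is a real extra route.

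**2. Possible size**

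Assume equal true event rates and events spread evenly over 52 weeks. Let v be the share captured by the common routes, t the share captured while therapists are visiting, and f the fraction of follow-up with therapist contact. Then

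ratio (enhanced : control) = [f·t + (1 − f)·v] / v = 1 + f·(t − v)/v.

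The protocol summary puts the intervention in the 16 weeks after surgery. Randomisation may come up to 4 weeks after surgery (section 7.3.1). So f lies between about 12/52 = 0.231 and 16/52 = 0.308. The values of v and t are assumptions.

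| v | t | f = 16/52 | f = 12/52 |
|---|---|---|---|
| 0.8 | 0.9 | 1.04 | 1.03 |
| 0.6 | 0.8 | 1.10 | 1.08 |
| 0.6 | 0.9 | 1.15 | 1.12 |
| 0.4 | 0.8 | 1.31 | 1.23 |

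Worked example for v = 0.6, t = 0.8, f = 16/52 and 100 true events per arm. Control records 60. Enhanced records 30.8 × 0.8 + 69.2 × 0.6 = 24.6 + 41.5, about 66.2. The ratio is 66.2/60 = 1.10.

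Two features could move f. Sessions start only after return home or permanent care-home admission, and their number varies (section 8.3), which lowers it. Events bunched in the early weeks would raise it. The documents give no timing.

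A cruder model lets therapists pick up a share x of otherwise missed events over the whole year, so that the ratio is 1 + (1 − v)·x/v. It gives 1.03 (v = 0.9, x = 0.25) to 1.50 (v = 0.5, x = 0.5). It ignores the limited contact window, so I treat its upper end as an outer limit only.

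**The case against.** A reader might infer from the footnote that controls are not monitored until 17 weeks. The documents do not support that. Section 9.2.1 covers both arms, section 10.8 runs from randomisation for each patient, and section 10.9 makes the site investigator responsible for all safety events. The footnote may only say who receives the intervention. This stands. What remains is a schedule that gives controls no marked monitoring point in that period and needs reconciling with the text.

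A reader might also infer that the count is certain to be biased, or that all safety endpoints are affected alike. Neither follows. The size rests on assumed capture rates and is small if recall is good. Usual-care therapists can also report events, and only some feasibility-trial controls had no community rehabilitation. Deaths, hospitalisations and falls with injury are serious events (section 10.3) and less easily missed. Admissions are also collected from everyone on the CSRI. No hypothesis test is set for endpoints 10 and 11, and each event is assessed for seriousness and causality. All of this stands and limits the point to mild events.

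Dropping therapist-reported events from the comparison would create the opposite bias. It could hide falls during therapy sessions, a harm that sections 3.2.5 and 10.6 both anticipate. That objection is sound, so those events should stay in the total.

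It may be said that form design and tabulation belong in the case report form and analysis plan, which are not shown. That holds for the tabulation. It does not settle who looks for events and when, which this protocol fixes differently by arm. If the source of a report is not collected, no later analysis can recover it.

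**Conclusion.** The point holds in a limited form. Both arms share a passive route and the 17- and 52-week collection, but the enhanced arm has an additional trained route, and the schedule conflicts with the text on monitoring during the intervention period. The count for endpoint 10, and to a lesser extent endpoint 11, is liable to be inflated in the enhanced arm for mild events. The ratio is about 1.03 to 1.3 under the assumed capture rates, which come from no figure in the protocol, with events spread evenly and therapist contact over 12 to 16 of 52 weeks. Deaths and admissions, and so endpoint 12, are little affected. The sample size is not touched.

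**What to change.** 1. Reconcile the section 9.1 schedule with sections 9.2.1 and 10.8, so that the same monitoring points apply to both arms.
2. State that the same set of adverse event questions is asked in both arms at the 17- and 52-week visits.
3. Record the source of each report (patient, carer, usual-care clinician, intervention therapist, records), unless the form already does so.
4. Present the between-arm comparison twice: for all events, and for events found by routes common to both arms (visits, CSRI, records). Keep therapist-only events, including any during therapy sessions, in the total and also list them separately.

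Therapist reporting and the 24-hour route for related serious events stay as they are. The cost is one extra form field, a few sentences in the protocol and a second tabulation.
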